#### **3.2.7.** Part 2 Secondary Endpoints

- Number and rate of HAE attacks
- Durability of response (attack rate trend over time)
- Number and proportion of days with angioedema symptoms
- Use of HAE attack medications
- Discontinuations due to lack of efficacy
- Durability in angioedema QoL questionnaire scores
- Durability in EQ-5D-5L scores
- Durability in TSQM scores
- Durability in WPAI scores

#### **3.2.8.** Part 3 Primary Endpoints

- Number and proportion of subjects with a TEAE
- Number and proportion of subjects who discontinue due to a TEAE
- Number and proportion of subjects who experience a TESAE
- Number and proportion of subjects who experience a Grade 3 or 4 TEAE
- Number and proportion of subjects who experience a treatment-emergent Grade 3 or 4 laboratory abnormality
- The proportion of subjects with a treatment-emergent, treatment-related AE consistent with a drug rash

#### 3.2.9. Part 3 Secondary Endpoints

- Number and rate of HAE attacks
- Durability of response (attack rate trend over time)
- Number and proportion of days with angioedema symptoms
- Use of HAE attack medications
- Discontinuations due to lack of efficacy
- Durability in AE-QoL questionnaire scores
- Durability in EQ-5D-5L scores
- Durability in TSQM scores
- Durability in WPAI scores

# 4. STUDY DESIGN

# 4.1. Summary of Study Design

This is a Phase 3, randomized, double-blind, placebo-controlled, parallel-group, 3-part study. Part 1 is designed to test the hypothesis that the HAE attack rate during 24 weeks of prophylactic BCX7353 will be less than that observed during 24 weeks of placebo. The primary efficacy endpoint will be assessed after the last subject completes Part 1 (through Week 24). Part 2 is designed to primarily evaluate the long-term safety of BCX7353 at 2 dosage levels. Part 3 is open-label and designed to primarily evaluate the long-term safety of BCX7353. Parts 1, 2, and 3 will be conducted in sequence, with Parts 2 and 3 conducted as continuous roll-overs from Parts 1 and 2, respectively. All subjects will receive BCX7353 in Parts 2 and 3, including those randomized to receive placebo in Part 1.

# Part 1 (24-week evaluation of blinded efficacy and safety data)

Subjects with HAE Type 1 or 2 will be eligible for the study following assessment of data obtained from screening procedures, including demonstration of a minimum number of attacks

documented during a prospective run-in period of 2 to 8 weeks from the date of the screening visit.

Approximately 96 treatment-eligible subjects will receive study drug (BCX7353 or placebo) in Part 1 of the study based on randomization in a 1:1:1 ratio into 1 of 3 treatment groups:

Group 1 (N = 32): BCX7353 110 mg administered orally QD for 24 weeks

Group 2 (N = 32): BCX7353 150 mg administered orally QD for 24 weeks

Group 3 (N = 32): Placebo administered orally QD for 24 weeks

Enrollment into treatment groups will be stratified by the baseline HAE attack rate ( $\geq 2$  attacks/month vs. < 2 attacks/month).

Qualifying attacks for eligibility determination are characterized as follows:

- The attacks must occur during the run-in period of 56 consecutive days, starting on the day of the screening visit
- The attacks are unique, defined as an attack that does not begin within 48 hours of the end of a previous attack.
- The attacks must have either been treated, required medical attention, or be documented to cause functional impairment, based on the subject's entry in the electronic diary (e-diary). Functional impairment is defined as the subject not being able to perform his or her daily activities without restriction (ie, subject records that he/she is at least slightly restricted in daily activities during the HAE attack).
- The attacks must include symptoms of swelling. Symptoms of swelling, in addition to visible swelling, may also include symptoms in the oropharyngeal or abdominal regions, which are indicative of internal swelling.
- The attacks are otherwise confirmed by the Investigator to be HAE attacks.

Once the subject records 2 such attacks, he or she may be randomized to study drug beginning on or after Day 28 of the run-in period; subjects who have at least 3 such attacks may be randomized to study drug beginning on or after Day 14 of the run-in period. A study schematic can be found in Figure 1.

Beginning at screening and through the Week 48 visit, details of acute attacks of angioedema will be recorded in an electronic diary (e-diary). Attacks will be treated in accordance with the subject's normal standard of care. Within approximately 2 business days of the end of each attack that occurs from the screening visit through the Week 48 visit, subjects will be contacted by the Investigator (or appropriately trained designee) to discuss the clinical characteristics of the attack, any questions on the entered data or to gain additional attack details not included in the e-diary that the Investigator deems important to clinically evaluate the event, as applicable. This information, in conjunction with the e-diary record, will be used by the Investigator to verify or reject the event recorded in the diary as an HAE attack. All Investigator-confirmed attacks of HAE must include symptoms of swelling; prodromal symptoms in the absence of swelling are not considered HAE attacks, regardless of treatment. Symptoms of swelling, in addition to visible swelling, may also include symptoms in the oropharyngeal or abdominal regions, which are indicative of internal swelling.

The main study will be comprised of adult subjects ( $\geq 18$  years of age); a substudy in participating regions will allow adolescent subjects ( $\geq 12$  to 17 years of age) to enroll. Main study and substudy subjects will be randomized via a separate randomization scheme; however, study-mandated procedures will be identical, and the analyses will include all subjects who participate in the study.

Study visits in Part 1 will occur at screening, baseline and Weeks 2, 4, 8, 12, 18 and 24. The primary efficacy analysis will occur after the last subject completes the Week 24 visit and will include all data through Week 24. Subject treatment will remain blinded to the subjects, site staff, and Sponsor staff who interact with sites on a regular basis during Part 2.

# Part 2 (24-week evaluation of safety of blinded BCX7353)

Part 2 of the study will start with the administration of study drug dispensed at the Week 24 visit. Subjects in Groups 1 and 2 will continue to receive the same BCX7353 dose to which they were randomized in Part 1 of the study in a blinded manner. Subjects randomized to Group 3 will undergo a second randomization in a 1:1 ratio to receive either a 110 mg QD dose or 150 mg QD dose of BCX7353 in a blinded manner beginning at the Week 24 visit (see Figure 1). The active dose a subject receives in Part 2 will be blinded for all subjects; subjects will be informed that they will receive an active dose of BCX7353 in Part 2.

Study visits in Part 2 will occur during Weeks 26, 28, 32, 36, and 48 with telephone contact at Weeks 40 and 44. Subjects will continue to document all angioedema attacks that occur while on study drug in their e-diary. Investigator confirmation of attacks will continue to be required for Part 2. Interim safety analyses will be conducted while Part 2 is ongoing to support regulatory filings.

# Part 3 (48-week evaluation of safety of open-label BCX7353)

Part 3 of the study will start with the administration of the study drug dispensed at the Week 48 visit. Subjects will continue to receive the same BCX7353 dose in Part 3 to which they were randomized in Part 2 of the study in an open-label manner. Once Part 1 results are available, all subjects in Part 3 may be moved to a single dose level of BCX7353, based on the data from Part 1, if appropriate.

Study visits in Part 3 will occur during Weeks 60, 72, 84, and 96, with telephone contact at Weeks 52, 56, 64, 68, 76, 80, 88, and 92.

Subjects will continue to document all angioedema attacks that occur in a paper diary throughout Part 3 and will have regular visits to assess safety and tolerability. Investigator confirmation of attacks will not be required for Part 3. All attacks recorded by the subjects will be reviewed and confirmed or rejected according to a set of pre-defined rules prior to inclusion in effectiveness analyses. These rules, which were constructed in concert with HAE-treating physicians, will be outlined in this SAP.

A final study follow-up visit will be scheduled approximately 3 weeks following the last administration of study drug (Week 99).

#### BCX7353-302 29 January 2019

#### Figure 1: Study Schema

Abbreviations: QD = once daily.

# 4.2. Definition of Study Drugs

BCX7353 110 mg QD is supplied as two 55-mg capsules of BCX7353 per dose for Parts 1 and 2 and as one 110-mg capsule of BCX7353 per dose for Part 3.

BCX7353 150 mg QD is supplied as two 75-mg capsules of BCX7353 per dose for Parts 1 and 2 and as one 150-mg capsule of BCX7353 per dose for Part 3.

Placebo QD is supplied as 2 capsules of matching placebo per dose.

# 4.3. Sample Size Considerations

# 4.3.1. Sample Size Justifications

The pooled standard deviation (SD) of the attack rate during effective dosing period (Days 8 to 28) in Study BCX7353-203 was 0.55. The observed treatment difference between the BCX7353 125 mg dose with dihydrochloride salt (equivalent to the 110 mg free base dose for the current study) and placebo for the effective dosing period using the full analysis population was 0.70 attacks/week, which represented a 73.8% reduction in attack rate from the placebo group.

Assuming a normalized placebo attack rate of 1 unit and a common SD of 0.55 units for BCX7353 and placebo attack rates, a sample size of 32 subjects will have 94% power to detect a 50% attack rate reduction (a treatment difference of 0.5 units) between BCX7353 and placebo, based on a 2-sided test at significance level of 0.05.

Sample sizes were increased to approximately 40 subjects for each active treatment group and placebo, to conservatively account for a potential dropout rate of 20%. Initial sample size calculations at the time the protocol was written did not allow for dropout.

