# 4.3.2. Sample Size Re-estimation

A blinded sample size re-estimation was originally planned to address uncertainty of the variability in the SD of the HAE attack rate. An interim analysis may have been performed after 50% subjects completed 24 weeks to provide the SD of the attack rate based on pooled data. Based on the pooled SD, the sample size may have been re-estimated to maintain at least 90% power to detect a 50% attack rate reduction. The study would have remained blinded, and the interim analysis would have been based on pooled data for sample size re-estimation. The final sample size was to be the maximum of either the initial sample size or the re-estimated sample size.

Due to rapid enrollment of study subjects, the sample size re-estimation was not performed.

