## 8.5. Multiple Comparisons and Multiplicity

There are 4 endpoints being tested. For each endpoint, there are 2 potential doses to be tested against placebo. The Type I error rate will be controlled at the study level by using a combination of hierarchical testing and the Hochberg procedure. The 4 endpoints will be tested in a hierarchical fashion, and the 2 doses will be tested using the Hochberg step-up procedure at each level of the hierarchy to which both doses progress through the hierarchy.

The first endpoint to be tested is the primary endpoint, the rate of investigator-confirmed HAE attacks during dosing in the entire 24-week treatment period of Part 1. Using the Hochberg step-up procedure, each of the 2 doses will be tested at the  $\alpha = 0.05$  level, comparing active treatment to placebo. If the maximum of the 2 p-values is < 0.05, the null hypotheses of no difference between the rate of attacks for subjects on active and placebo treatment will be rejected for both doses and testing will proceed to the next endpoint in the hierarchy with  $\alpha = 0.05$ . If the maximum of the 2 p-values is > 0.05 but the minimum of the 2 p-values is < 0.025, the null hypothesis for the dose with p < 0.025 will be rejected and testing for that dose only will proceed to the next endpoint in the hierarchy with  $\alpha = 0.025$ . Otherwise, the null hypotheses for both doses will not be rejected, testing will stop, and the next endpoint in the hierarchy cannot be tested.

The first, second, third, and fourth endpoints in the hierarchy are:

- 1. The rate of investigator-confirmed HAE attacks during dosing in the entire 24-week treatment period (Day 1 to Day 168)
- 2. Change from baseline in AE-QoL at Week 24 (total score)
- 3. Number and proportion of days with angioedema symptoms through 24 weeks
- 4. Rate of investigator-confirmed HAE attacks during dosing in the effective treatment period (beginning on Day 8 through 24 weeks)

The process described above will be continued for each endpoint in the hierarchy until either all 4 endpoints have been tested or testing has stopped due to non-rejection of the null hypotheses for both doses for endpoints earlier in the hierarchy. At each level of the hierarchy, the Hochberg step-up procedure is used to control Type I error rates if 2 doses are to be tested. Otherwise, if only 1 dose is being tested, the single test is conducted with  $\alpha = 0.025$ .

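### The 94% power in SAP 4.3.1 follows from its declared inputs, but those do not match the Study 203 figures or the Hochberg test; at 32 per group, power is about 91.5% per dose if both doses work and 88% if only one does

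*SAP*

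**What the plan says.** Section 4.3.1 of the SAP (Study BCX7353-302) takes its planning values from Study BCX7353-203: a pooled SD of 0.55 for the attack rate over Days 8 to 28, with no unit printed, and a difference from placebo of 0.70 attacks/week at the equivalent of the 110 mg dose, described as a 73.8% reduction. It then changes scale: "Assuming a normalized placebo attack rate of 1 unit and a common SD of 0.55 units". From there it concludes that "a sample size of 32 subjects will have 94% power to detect a 50% attack rate reduction", "based on a 2-sided test at significance level of 0.05". The size is per group; Section 4.1 lists "Group 1 (N = 32): BCX7353 110 mg administered orally QD for 24 weeks". Section 4.3.1 goes on to raise the target to about 40 per group for a possible 20% dropout, and Section 15 records that change.

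Section 4.3.1 does not mention multiplicity, and it does not say whether 94% is the power for a lone dose, for each of two effective doses, or for both together. Section 8.5 tests the two doses by Hochberg. Both are rejected if the larger p-value is below 0.05. "If the maximum of the 2 p-values is > 0.05 but the minimum of the 2 p-values is < 0.025", only the dose with the smaller p-value is rejected.

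**The concern.** There are two mismatches. First, the placebo rate was rescaled to 1 but the SD kept the same number, 0.55. Dividing a rate by a constant divides its SD by that constant too. Second, the calculation uses one comparison at 0.05, whereas the planned test can hold a dose to 0.025, depending on what the other dose does.

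Both mismatches make the stated power look better than the section's own source figures support. The blinded re-estimation that would have checked the SD was not performed (Sections 4.3.2 and 15), so 4.3.1 is the only power justification left in the SAP. What is at stake is the accuracy of a reported design property. The tests and patient numbers do not change.

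**Working it through.** **Inputs.** From Section 4.3.1: n = 32 per group, difference 0.5, SD 0.55, two-sided 0.05, Study 203 difference 0.70 attacks/week, Study 203 reduction 73.8%, dropout 20%. From Section 8.5: the Hochberg rule. Assumed: the 0.55 is in attacks/week, the only rate unit in that paragraph.

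**Step 1: reproduce the stated figure.** For a two-sample t-test, the noncentrality is difference / (SD × √(2/n)) = 0.5 / (0.55 × √(2/32)) = 0.5 / 0.1375 = 3.64, with 62 degrees of freedom. Two-sided power at 0.05 is 94.7% (normal approximation 95.3%). A one-sided test would give 97.7%, so the two-sided reading is the one that matches 94%. The dropout step also checks: 32 / (1 − 0.20) = 40.

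**Step 2: put the SD on the normalized scale.** Placebo rate in Study 203 = 0.70 / 0.738 = 0.949 attacks/week. SD in units of the placebo rate = 0.55 / 0.949 = 0.580. Noncentrality = 0.5 / (0.580 × 0.25) = 3.45, and power at 0.05 is 92.4% (normal 93.2%). Allowing for rounding in the printed inputs, the placebo rate lies between 0.941 and 0.956, the SD between 0.570 and 0.590, and power between 91.6% and 93.2%.

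**Step 3: apply the Section 8.5 rule.** Three arms with a shared placebo were simulated (200,000 trials per setting), with pairwise t-tests. A dose is rejected if both p-values are below 0.05, or if its own is below 0.025. An effective dose has a 50% reduction; in the lone-dose case the other dose is inert.

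| Per group | SD | Both work: power per dose | Both work: both rejected | One works: power for that dose |
|---|---|---|---|---|
| 32 | 0.55 | 94.2% | 90.9% | 90.9% |
| 32 | 0.58 | 91.5% | 87.1% | 87.6% |
| 40 | 0.55 | 97.8% | 96.4% | 96.3% |
| 40 | 0.58 | 96.4% | 94.2% | 94.2% |

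**Cross-check.** A fixed level of 0.025 at SD 0.58 gives 87.2% with 32 per group and 94.0% with 40. Both are slightly below the simulated lone-dose values, as expected: an inert partner occasionally passes 0.05, and the effective dose then needs only 0.05. Over the rounding range of the SD, the fixed-0.025 power at 32 runs from 86.0% to 88.4%.

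**The case against.** The strongest reply is that nothing has been miscalculated. The declared inputs yield the declared power, and 0.05 is Hochberg's first step, so 0.025 is not the general test level. With SD 0.55 and both doses at the planned 50% effect, the actual Hochberg rule gives 94.2% per dose, which is the stated figure. The drop to about 88% needs one dose to be inert, yet Study 203 showed a 73.8% reduction at the equivalent of the lower dose and the plan cautiously assumes 50%. All of this stands. It limits the Hochberg point to an omission that matters mainly if only one dose works.

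It can also be said that the SD unit is inferred. That is true. If 0.55 were already a multiple of the placebo rate, the SD 0.55 rows of the table would apply, and only the silence about Hochberg would remain.

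Further, the target is about 40 per group, and the primary analysis includes on-treatment data from subjects who stop early, with log duration as an offset (Sections 6.5.3 and 8.6.1). The effective size therefore probably lies between 32 and 40. This stands too, although 32 is the size to which the section attaches its 94%, and Sections 4.1 and 4.4.1 still print 32 per group or 96 in all.

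Finally, the SD comes from a three-week window, while the endpoint covers 24 weeks and is analysed by Poisson regression. A longer window should reduce the SD of a subject's rate. Every figure here, the SAP's included, is therefore a t-test approximation.

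**Conclusion.** The point holds as a small correction to a stated figure. The 94% follows from the inputs as declared, but it does not survive once the SD is put on the same scale as the placebo rate and the Section 8.5 test is applied. At 32 evaluable per group, power is then about 91.5% per dose if both doses work, about 88% if only one works, and about 87% to reject for both. This rests on the SD being in attacks/week, on a 50% reduction for each effective dose, and on a t-test standing in for the Poisson model. The protocol supplied is for Study BCX7353-202, so the sample size text of the Study 302 protocol could not be checked.

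A reader might infer three stronger things that the documents do not support:

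- That the arithmetic is wrong. It reproduces.
- That the trial is underpowered. With 40 analysed per group, power is about 96% per dose if both work and 94% for a lone dose.
- That the plan breaches a 90% minimum of its own. Section 4.3.2 says "the sample size may have been re-estimated to maintain at least 90% power", but that was the target of a re-estimation that did not take place, and no multiplicity rule or lone-dose case was attached to it.

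**What to change.** In Section 4.3.1:

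- State the unit of the Study 203 SD. If it is attacks/week, use about 0.58 on the normalized scale.
- Say that the two doses are tested by the Hochberg procedure of Section 8.5, and name the power being reported.
- Give power for one and for two effective doses: at 32 evaluable per group, about 88% for a lone dose, 91.5% per dose and 87% for both; at 40 analysed per group, about 94%, 96% and 94%.
- Note that these are t-test approximations to the planned Poisson regression.

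The cost is a slightly less favourable stated figure at 32 per group. The change is to wording only: no added patients, and no change to the tests or the target of about 40 per group.

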# 4.3.2. Sample Size Re-estimation

A blinded sample size re-estimation was originally planned to address uncertainty of the variability in the SD of the HAE attack rate. An interim analysis may have been performed after 50% subjects completed 24 weeks to provide the SD of the attack rate based on pooled data. Based on the pooled SD, the sample size may have been re-estimated to maintain at least 90% power to detect a 50% attack rate reduction. The study would have remained blinded, and the interim analysis would have been based on pooled data for sample size re-estimation. The final sample size was to be the maximum of either the initial sample size or the re-estimated sample size.

Due to rapid enrollment of study subjects, the sample size re-estimation was not performed.

# 4.4. Randomization

Subjects will be randomized via the interactive response system (IXRS). Details on the processes followed for randomization are provided in a separate manual.

#### 4.4.1. Part 1 Randomization

Approximately 96 subjects will be randomized in a 1:1:1 (active:active:placebo) ratio to 1 of the following treatments in Part 1:

- Group 1: BCX7353 110 mg administered orally QD for 24 weeks
- Group 2: BCX7353 150 mg administered orally QD for 24 weeks
- Group 3: Placebo administered orally QD for 24 weeks

Enrollment into treatment groups will be stratified by the site-calculated baseline HAE attack rate ( $\geq 2$  attacks/month vs. < 2 attacks/month). The site-calculated baseline attack rate must have been provided during randomization and was to be calculated as:

Number of HAE attacks meeting baseline criteria from Screening to Randomization × 28 Randomization Date – Screening Date + 1

HAE attacks to be utilized in calculation of the baseline attack rate must meet the following criteria:

- The attacks must be unique, which is defined as an attack that does not begin within 48 hours of the end of the previous attack.
- The attacks must have either been treated, required medical attention, or have been documented to cause functional impairment based on subject entry in the e-diary. Functional impairment is defined as the subject being unable to perform daily activities without restriction (ie, subject records that he/she is at least slightly restricted in daily activities during the HAE attack).
- The attacks must include symptoms of swelling. Symptoms of swelling, in addition to visible swelling, may also include symptoms in the oropharyngeal or abdominal regions, which are indicative of internal swelling.
- The attacks must be confirmed by the Investigator to be HAE attacks. Subjects will be contacted within 2 business days of the attack to discuss the attack and to resolve any Investigator queries on the entered data in the e-diary, as applicable.

# 4.4.2. Part 2 Randomization

At the Week 24 visit, subjects originally randomized to placebo in Part 1 will be randomized in a 1:1 (active:active) ratio to receive a 110 mg QD or 150 mg QD dose of BCX7353 in Part 2 (see Figure 2). Subjects will continue to receive the same dosing regimen received in Part 2 during Part 3. Once Part 1 results are available, all subjects in Part 3 may be moved to a single dose level of BCX7353, based on the data from Part 1, if appropriate.

